4.3 Phase 1: Design and Development of the Virtual Reality Experience

Objective 1: Work with an interdisciplinary team to collaboratively develop a prototype that simulates the MRI environment and experience at BCCH in VR.

The media will be co-developed with a multidisciplinary team of stakeholders, including patient and family partners. Considerations for designing the resource have been informed by Gitlin (2013).²² In principle, the developed media will integrate an animated character that will guide the user through a series of tasks. The user will be encouraged to pivot, rotate, and semi-independently explore the virtual environment. The virtual environment will be created using any combination of 360 video and UNITY, a cross-platform game engine used for 3D environments (**Table 3**).

Table 3. Considerations for designing the VR media, adapted from Gitlin (2013).²²

Domain	Program Elements
Target of Intervention	Individual Family and social network
Area Targeted	Reduce anxiety and non-compliant behaviours that necessitate sedation Increase knowledge about the MRI procedure and environment Improve skills required for successful MRI (e.g. holding breath)
Delivery Technique	Multiple iterations, tailored to children of different age groups (4-12 and 13-18 years) and their caregivers Needs assessment driven
State of intervening	Prevention of sedation
Delivery mode	Virtual Reality Booklet Mock MRI
Dose and intensity	Frequency of contact (TBD) Length of time engaging (TBD)
Immediate and potential delivery setting	Hospital, clinic, or medical office (immediate) Mobile technology (immediate) Home (potential) Community (potential)
Characteristics of interventionists	Self-Guided delivery
Potential funding streams to support the intervention if proven effective	Costs associated with training (TBD) Costs associated with technology (TBD) Cost benefit to healthcare systems (TBD)

We have elected to use Google Pixel and MERGE VR as primary deployment hardware due to its balance of quality and affordability, given this specific use-case. The use of a mobile phone to view the content will allow for use in more affordable VR mechanisms in the future (i.e. Google Cardboard, a self-assembly cardboard version of a VR viewer), and easy transport to community or home-based settings (i.e. Cardboard mechanism is sent with instructions to end-users to assemble and launch app on their personal device at home). Movement throughout the platform will be facilitated through one (or a combination) of the following options, decided in collaboration with stakeholders:

1. Continuous Motion: the user has no control of travel
2. Magnetic Switch: the user can be stopped and started using a toggle switch
3. Bluetooth Controller: the user is in direct control of forward and backward travel

The program will be designed and continuously evaluated using the Plan-Do-Study-Act (PDSA) cycle, and created in the steps following the Technology Readiness Scale (TRL).²³ Specifically, our project focuses on progressing through phases 2 through 5 (**Figure 1**).

[figure not shown]

Figure 1. Technology Readiness Level scale.²³

The Virtual Reality Simulation

The VR intervention is underpinned by experiential learning and social cognitive theory, such that experience and accomplishments obtained through observation of successful performance and simulation in the VR experience will encourage imitation and reinforce success in the real MRI experience.²⁴ The VR tour will introduce and explain the preparation and procedure of MRI scans within the BCCH medical imaging centre. Users will be able to turn, pivot, and explore the virtual room. The video will be at an appropriate length to ensure the pace can be followed by younger children, but will allow users to pause or stop at any point, to reduce the potential for motion sickness, headaches, or dizziness.¹⁷

Patients and families will be directly involved in the development of the resource to ensure the content is effectively tailored, relevant, and generalizable to practice settings. An advisory group will be developed to help guide this project and support content development and clinical validation – group membership includes Child Life Specialists,

Physicians, Nurses, Psychologists, Health Literacy Specialists, Media Developers, and others (to be determined).

Any medical staff depicted in the virtual world will be dressed in common professional attire to improve realism. An animated character will guide the user in the tour. Filming will be dependent on access to resources, but will likely be carried out using GoPro Fusion (360-degree camera) in the medical imaging facility at BCCH. The video components will then be stitched together, and the VR tour will be available using a variety of low-cost VR systems, accessible through a public-facing website. Since filming will occur in the hospital, it may occur over multiple iterations to ensure that patients and/or medical records are not inadvertently filmed.

To promote the self-guided nature of our proposed delivery, the virtual interaction will begin with a tutorial explaining how to use the application. When ready, users will be invited to be virtually guided through the MRI procedure. They will be able to pause the experience at any time. The content may include experiences such as:

1. Entering the medical imaging facility
2. Preparing for the scan (e.g. changing into a gown, checking height/weight, removing metal)
3. Additional information will be provided about the procedure, including:
 - What MRI is and the sounds it will make
 - The importance of staying still
 - What intravenous contrast (GAD) is
 - What equipment to expect
 - i. Knee coils
 - ii. Head coil
 - iii. Hand coils
 - iv. Foot coils
 - v. Leg coils
 - vi. Body coils
 - vii. Shoulder coils
 - viii. Seatbelts
 - Other information, as identified
4. Receiving numbing cream, and an IV
5. Choosing if they want to be accompanied during the scan
6. The two MRI rooms
7. The opportunity to freely explore the room and medical devices, such as the MRI machine, the patient table, the murals on the walls, types of coils, and straps.

The character will also guide the user through the MRI sequence. Content may include:

1. Wearing ear protection and headsets
2. Watching a movie
3. Talking to the MRI Technologist out loud
4. Using the emergency call bell, if required
5. The control room where the Technologist goes
6. Laying on the table and being strapped into place using the coils and seatbelts
7. Entering into the bore of the MRI machine

8. The red light used to center the patient's body for the pictures
9. Starting and completing the scan (i.e. wait a pre-designated amount of time inside the bore, before easing the patient outside the scanner).
10. Receiving intravenous contrast liquid (if applicable)

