4.4 Phase 2: Technology Evaluation and Comparative Assessment

Objective 2: Evaluate the effectiveness of the VR simulation in preparing patients for MRI, and compare to other modalities (i.e. booklet, simulation with CLS).

Protocol for Evaluating the Virtual Reality MRI Simulator

The goal of Phase 2 is to evaluate the effectiveness of the intervention on the basis of its ability to prepare patients and families for the MRI procedure. To do so, this phase will establish evidence to investigate whether the VR intervention can be implemented to reduce anxiety and efficiently prepare children for non-sedated MRI scans. Our needs assessment has identified that new accessible behavioral interventions are both needed and desired to alleviate the anxiety and lack of preparation necessitating sedation during medical imaging with children who live afar, who are not mobile, and who need extra practice. Virtual preparation is a promising practice that has been found to be safe, feasible, and acceptable in multiple clinical care settings.^{12,13,16,20,25}

The project evaluation plan consists of comparing the current modes of delivery through an objective assessment of movement and inquiry into the acceptability and utility of the intervention components, including potential barriers to adherence or behavioral change that could have unintended consequences. This information will help to generate knowledge that can be used to refine the current prototype and support future innovation in this domain at BCCH (Phase 4, not included in this proposal).

[figure not shown]

Figure 2. Evaluation design.

The recruitment strategy has been informed by the literature on recruitment in pediatric research settings.²⁶⁻²⁸ The design and expansion of the recruitment strategy has enacted as a response to the low enrollment rate arising from traditional strategies (posters that we had initially proposed). Participants will be recruited through:

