A minimum of 93 participants (31 participants per group) aged 4-to-13 will be recruited through convenience sampling, consented, and randomized by staff to one-of-three preparation programs (VR, mock MRI, or booklet). Details of the comparison groups are outlined in **Table 4**. Given the restricted availability of the simulator, child life specialists, and the availability of participants, we are unable to fully randomly allocate participants. As such, participants will be randomly assigned to the intervention options available according to their individual availability (using Research Randomizer <https://www.randomizer.org/>). For example, if a participant is available on a Thursday that virtual reality and booklet are available, they will be randomly allocated to one of these interventions.

This phase will have open recruitment to all children and adolescents interested in participating, such that participants may not be BCCH patients scheduled for an MRI. This recruitment strategy was selected due to the resource constraints associated with limiting the evaluation group to MRI patients only.

Table 4. Details of the comparison groups.

	VR Simulation	MRI Preparation Booklet	Mock MRI
Facilitator	Research Assistant	Research Assistant	Child Life Specialist
Location	BCCH	BCCH	Simulation Room
Content	Refer to The Virtual Reality Simulation	Refer to MRI Preparation Book	Individualized intervention in physical simulator.

The different interventions will be held in separate private rooms located in BCCH, such that the VR and booklet groups will not have prior exposure to the imaging centre or the simulation room in advance of their assessment. This is to simulate our intended delivery in hospital, medical office, or clinic settings but minimize alternative explanations associated with testing in the simulation room where assessments will take place (previously described in **Table 3**).

Data will be collected throughout the implementation process (**Figure 3**). The predictive variables (demographics and relevant history, and delivery type) will be captured at the start of the session. The primary outcome variable is likelihood of success (pass/fail) of the MRI simulation, and will be measured at the end of the assessment. Anxiety will also be measured at three time points. Usability testing will be conducted throughout to capture possible quality improvements and amendments to each of the program delivery modes.

Inclusion/Exclusion Criteria

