- 9) Participants will be informed that they will now be completing a simulation test with the MRI scanner. Participants will be reminded of their free and informed ongoing consent.
- 10) The participant will be transferred to the simulation room, located in the medical imaging center at BCCH. Upon entering the simulation room, participants will verbally complete the VPT with staff (during test). In parallel, parents will complete the Short STAI on the iPad. (5 minutes)
- 11) Participants will be guided through a mock MRI and be assessed using MoTrack®, an objective head motion tracking system.³² The simulation will be completed over 20 minutes and will involve progression through the “MRI procedure”, remaining in the bore for 8 minutes. All participants will receive the same type of simulated scan. We will not be simulating any invasive procedures that can sometimes occur during the MRI (i.e. an IV or intravenous contrast liquid). Please note that this assessment involves a mock procedure using the simulator, not a real MRI.
- 12) Immediately following the simulation, participants will verbally complete the VPT with staff (post-test). In parallel, parents will complete the Short STAI on the iPad. (10 minutes).

- 13) Users will be asked to indicate on the *Smileyometer* how they thought the preparation activity was overall in preparing them for the MRI. Parents/guardians will be asked to complete the USE Questionnaire.
- 14) Staff will ask the user open-ended questions on the preparation materials according to three separate criteria of fun, ease of use, and how good it was for learning about the MRI experience. The final usability assessment will take a total of 10 minutes.
- 15) After the session is "complete", children will be told that they "happen to have some time left" so they can play with any of the preparation materials offered (VR, Mock MRI, Booklet) for 5-minutes if they want to "because they did so well during the activity." This will give children a natural choice selection and will be used to gauge preferences for the activities.
- 16) A verbal session debrief will include an opportunity for questions to mitigate any residual feelings of discomfort or anxiety that may arise from the project's activities.

Outcome Measures

The measures used to evaluate the intended outputs and outcomes associated with this project are outlined below (**Table 4**).

Table 4. Outputs and outcomes associated with the project.

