Measure	Immediate Outputs	Intended Outcome
Primary		
MoTrak®	# of participants "prepared" to be scheduled for an effective MRI	
Improve access to MRI preparation for children who:
 
 - Live out of town - Would like to practice skills at home - Have mobility issues 
Improve non-sedation rates for MRI scans.

Venham Pictoral Test & Short STAI	# of participants with reduced anxiety # of parents with reduced anxiety	
Improve access to MRI preparation materials.
 
Improve behavioral compliance during medical procedures.

Secondary		
Smileyometer	# of participants who find the delivery mode fun and engaging to use	
Improve acceptability of preparation materials.
 
Improve satisfaction.

USE Questionnaire	# of parents who find the preparation materials useful	
Improve acceptability of preparation materials.
 
Improve satisfaction.

Natural Choice Selection	# of participants who select the booklet # of participants who select the mock MRI # of participants who select virtual reality # of participants who select none	Identify preference for engaging. Identify frequency of contact and time engaging.
Length of Stay	Minutes spent per segment	Improve hospital efficiency
Guided Survey	# of participants who find the booklet fun, easy to use, and good for learning about the MRI experience # of participants who find the mock MRI fun, easy of use, and good for learning about the MRI experience # of participants who find the virtual reality game fun, easy of use, and good for learning about the MRI experience	Improve utility of MRI preparation materials. Identify frequency of contact and time engaging.
Interpupillary Distance	Average interpupillary distance per age	Improve headset configuration.

Primary Measures

Predictive Success in Avoiding Sedation

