For the purposes of this evaluation, we will define total LoS as the duration, in minutes, from starting the *preparation* segment to completion of the simulated *assessment*. Inter-segment times will also be recorded. Preparation time will be capped at 45 minutes. Assessment time will be capped at 20 minutes. Start of preparation will be noted as time when study staff finish describing the intervention and indicate it is time to begin the active preparation. Time will stop when the participant is “discharged” from the MRI simulation, before the natural choice selection exercise and debriefing process begins. Time spent transitioning between activities or breaks required for reasons unrelated to the evaluation will not be counted towards overall LoS.

Interpupillary Distance

Interpupillary Distance will assume normal conditions and be measured objectively before preparation using Pryor's (1969) method³⁶ to ensure appropriate set up of the virtual reality device.

[figure not shown]

FIG. 1. Formula for interpupillary distance.

Usability Testing

The Smileyometer – 1 minute

The Smileyometer^{30,31} is an instrument used for measuring the opinions of technology in children, and has been validated in multiple studies assessing educational materials and software. The Smileyometer is based on the Visual Analogue Scale,³⁷ consisting of a 5-point Likert scale that uses pictorial representations. Participants are asked to point to the face they relate to.

Guided Survey – 10 minutes

The RA will ask the participant several open-ended questions on the preparation materials according to three separate criteria of fun, ease of use, and how good it was for learning about the MRI experience.

USE Questionnaire – 10 minutes

The USE Questionnaire²³ will be administered to the parents/guardians after the mock MRI only. This will allow participants to compare the VR application to the “effective MRI” experience. The USE Questionnaire is a 7-point Likert rating scale that has been well-validated to assess a program’s usefulness, ease-of-use, ease of learning, and satisfaction.

Analysis and Interpretation

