A priori power analysis was calculated using G-Power.³⁸ A total sample size (N) of 93 was calculated to be needed across the 3 groups (31 per group), with a significance level of 95% ($\alpha=0.05$) and a power of 90% ($\beta=0.10$), allowing for a 10% drop out rate. An effect size of 0.2 was selected to reflect the research suggesting that CLS preparation can reduce sedation rates by 20%.

Descriptive analysis will be conducted on the demographics and relevant history data.

Differences in predictive success of the MRI simulation ranking scores (pass or fail) will be examined using a Repeated Measures ANOVA, within-between interaction for three timepoint measurements (before, during, after) of anxiety and delivery type (VR, mock MRI, booklet). In the case of an off-normal distribution, non-parametric tests may be used. Multivariate analysis will test for possible confounding effects (demographics and relevant history).

Survey data (USE questionnaire, Smileyometer) will be analyzed using means and standard deviations of all respondents for each category of the questionnaires. The proportions of the participants reporting high, medium, or low levels will also be calculated.

Study staff will document responses to the guided survey and read the recorded answers back to participants to verify accuracy and elicit possible further reflection. All of the qualitative data will be uploaded to NVivo by study staff. When complete, study staff will code the information to identify major themes, gaps, barriers within the existing approach and the team will devise recommendations for improving the preparation programs. The phases of this process include:

- Familiarizing yourself with the data

- Generating initial codes
- Searching for themes
- Reviewing themes
- Defining and naming the themes
- Triangulation with other findings and producing a report

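### Phase 2 has no listed record of VR symptoms or of why a child stopped, so symptom-related stopping cannot be counted by arm and looks like quick completion in Length of Stay

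*Combined protocol and SAP*

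**What the plan says.** Section 4.3 (The Virtual Reality Simulation) states that the VR video "will allow users to pause or stop at any point, to reduce the potential for motion sickness, headaches, or dizziness". This is a design feature that lowers a recognised risk; it is not an endpoint.

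Section 4.4 (Protocol for Evaluating the Virtual Reality MRI Simulator) describes the evaluation as movement assessment together with "inquiry into the acceptability and utility of the intervention components, including potential barriers to adherence or behavioral change that could have unintended consequences", with the aim of refining the prototype.

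The routes that could carry such information are:

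- **Usability testing** (section 4.4, data collection paragraph): "Usability testing will be conducted throughout to capture possible quality improvements and amendments to each of the program delivery modes".
- **Guided survey** (Implementation Plan, step 14): "open-ended questions on the preparation materials according to three separate criteria of fun, ease of use, and how good it was for learning". Under Analysis and Interpretation the answers are read back to the child, and "study staff will code the information to identify major themes, gaps, barriers within the existing approach".
- **Length of Stay**: the outcome table lists its output as "Minutes spent per segment". Its definition caps preparation at 45 minutes and adds that "breaks required for reasons unrelated to the evaluation will not be counted towards overall LoS".
- **PDSA cycle** (section 4.3): continuous evaluation of the program, with no data items given.

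**The concern.** Tolerability is one of the more obvious reasons why a child might not get through a headset-based preparation. It bears on acceptability, which Phase 2 sets out to examine. The intended delivery is self-guided, in clinics and potentially at home (Table 3), where no research assistant would be present.

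Two things are at stake. First, the trial could report who passed, how anxious they were and what they preferred, but not how many VR children had the symptoms that the plan names or stopped because of them. Analysts cannot recover this after the session. Second, Length of Stay is read as an efficiency outcome (outcome table). It supplies the time estimates for activity-based costing (section 4.5, Stage 1) and is among the outcomes carried into the economic analysis (Stage 2). A stop caused by intolerance would enter there as a shorter, cheaper preparation.

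**Working it through.** The point is an absence, so the first check is a reading of every place where the data could be collected.

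1. **Steps 1 to 16.** Staff administer consent, anxiety scales, the Smileyometer, interpupillary distance, the activity, the mock scan, the USE Questionnaire, the guided survey, the free choice and a debrief. None includes a symptom item or a stop reason. The debrief offers a chance to raise discomfort, but no recording is described.
2. **Outcome table.** The rows are MoTrak, Venham and Short STAI, Smileyometer, USE, natural choice, Length of Stay, guided survey and interpupillary distance. There is no tolerability row.
3. **Measure definitions.** The USE Questionnaire goes to parents and covers usefulness, ease of use, ease of learning and satisfaction. The data collection form is described as demographics and history.
4. **Analysis and Interpretation.** No summary of symptoms or stopping is planned. Coded open-ended answers give themes. A complaint that a child happens to volunteer is not a numerator for a rate by arm.
5. **Length of Stay.** Minutes are recorded without a reason. Because 45 minutes is a ceiling and not a required dose, a short preparation may mean that the child finished or that the child gave up. The break rule requires staff to judge why a break occurred, but no field is listed to keep that judgement.

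The second check is what a log could deliver. The plan gives 31 children per group and a 10% dropout allowance, so 31 × 0.9 ≈ 28 completers. The documents give no symptom rates; those below are assumptions.

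- Zero cases, one-sided 95% upper limit, 1 − 0.05^(1/n): n = 31 gives 9.2%; n = 28 gives 10.1%.
- Chance of at least one case, 1 − (1 − p)^n:

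| Assumed true rate of recorded cases | n = 31 | n = 28 |
|---|---|---|
| 2% | 46.5% | 43.2% |
| 5% | 79.6% | 76.2% |
| 10% | 96.2% | 94.8% |

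- Three of 31 would be 9.7%, exact 95% interval 2.0% to 25.8%. Against none of 31 in the booklet arm, two-sided Fisher p = 0.24.

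The third check is whether a prompted question would fit in the two-hour session. Stated times for steps 2, 3, 7, 8, 10, 11, 12, 13–14 and 15 are 5 + 5 + 45 + 1 + 5 + 20 + 10 + 10 + 5 = 106 minutes. One minute for the step 5 Smileyometer makes 107. That leaves 120 − 107 = 13 minutes for untimed steps 1, 4, 6 and 9, the transfer in step 10, and step 16. If the 10-minute USE Questionnaire runs outside the step 13–14 total and not in parallel, 3 minutes remain. A question at step 16 would also ask the child to look back 1 + 5 + 20 + 10 + 10 = 46 minutes to the end of preparation (51 with the step 15 play), or 91 to 96 minutes to its start, plus the untimed steps.

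**The case against.** The strongest reply is that the plan promises a qualitative inquiry and delivers one. Open-ended questions, read-back and coding for barriers are a legitimate method, and nothing in section 4.4 promises symptom rates by arm. That stands: a reader might infer that the Phase 2 commitment is broken, but the documents do not support this. The commitment is partly met; what is missing is a way to count.

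A second reply is that risk is already handled. Section 4.4 cites evidence that virtual preparation is safe, feasible and acceptable in several clinical settings. It excludes children with seizures, epilepsy or head wounds, measures interpupillary distance for headset set-up, and puts a research assistant with the VR child. These are reasonable safeguards, so it would be wrong to say that safety was ignored. They reduce the risk but do not record what happens with this prototype.

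A third reply is that early stopping has no meaning when 45 minutes is only a cap and a booklet has no pause button. This is correct, and the fix must define completion for each arm. The break rule is also a side issue: a break caused by VR symptoms would not ordinarily count as unrelated to the evaluation, so the exclusion does not by itself hide such breaks.

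Finally, the wording of the guided survey, Figures 2 and 3 and the consent pages could not be seen. A form there cannot be excluded. If one exists, the sponsor need only cite it and add the reporting row.

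**Conclusion.** The point holds as a gap in data capture. No listed step records a symptom or a reason for stopping, so symptom-related stopping cannot be counted by arm, and Length of Stay cannot separate intolerance from quick completion.

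A reader might go further and infer that the trial fails an objective or that the comparison of arms is compromised. Neither follows. Tolerability is not among the objectives in section 4.2, and the missing items do not enter the pass/fail or anxiety outcomes. Nor do the documents show that a prompted symptom question is needed: at the debrief it would rely on long recall in children from age 4, after a mock scan and possibly further VR, in a session not shown to have room.

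The benefit of closing the gap is modest. With 31 VR children, a problem that produced a logged case in 10% of them would very probably appear at least once (96%), while one at 2% would be missed more often than not. These figures assume independent children and the assumed rates; under-reporting would lower the chance of detection and make a zero count less reassuring.

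**What to change.** At step 7, in all three arms, have the existing facilitator (research assistant or Child Life Specialist) log:

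- any symptom volunteered or observed;
- any stop before the content is finished, with its time and reason. Define finished as the end of the VR tour, the end of the booklet, or the Child Life Specialist's judgement that the mock MRI session is complete.

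Add one descriptive row to the outcome table: number per arm with any logged symptom, and number stopping before completion with reason. Flag these children in the Length of Stay summary and in the Phase 3 costing time estimates. Report counts with exact intervals and no test between arms.

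The cost is a short staff note per child during an activity that is already supervised. Nothing is asked of the child, so the primary measures and the step 15 preference measure, where "This will give children a natural choice selection and will be used to gauge preferences for the activities", are left alone. The main downside is likely under-reporting, because symptoms are not prompted; the report should say so. A prompted question is optional if session time allows. If it is used, ask it in all arms after the step 15 choice has been recorded, and identify children who used VR in step 15.
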